16.5 Investigator Responsibilities	25
17 REFERENCES.....	26

LIST OF ABBREVIATIONS

AE	adverse event
CFR	Code of Federal Regulations
CRF	case report form
DMC	Data Monitoring Committee
DSMB	Data Safety Monitoring Board
FDA	Food and Drug Administration
GCP	Good Clinical Practice
HIPAA	Health Insurance Portability and Accountability Act of 1996
ICF	Informed Consent Form
ICH	International Conference on Harmonization
IRB	Institutional Review Board
PI	Principal Investigator
SAE	Serious Adverse Experience
SAP	Statistical Analysis Plan
UCSF	University of California, San Francisco
US	United States
	VAS (Visual Analog Scale)
	ICHD (International Classification of Headache Disorders)

PROTOCOL SYNOPSIS

TITLE	The CHOCOLATE Study: CHOCOlate MeLatonin for AdolescenT MigrainE
SPONSOR	Investigator Initiated Study ([name])
FUNDING ORGANIZATION	Funding is provided by the UCSF Pediatric Headache Program discretionary funds, and the product is donated by Good Day Chocolate
NUMBER OF SITES	1
RATIONALE	
Migraine is common in children and adolescents.
 
It causes pain and suffering and disability.
 
Acute medications exist but do not work for everyone and may cause side effects. Some patients and parents will prefer a natural supplement for acute treatment rather than a prescription or over-the-counter pharmacologic agent.
 
Melatonin has recently been shown to be effective for migraine prevention in adults and some early work suggests it may also be effective for migraine prevention in children and adolescents. Some migraine treatments that are helpful as preventives can also be helpful acutely. This is a dose-finding study to begin to examine whether melatonin might also be helpful acutely for treating migraine in children and adolescents.

STUDY DESIGN	This pilot randomized trial is a dose-finding study to determine which dose of melatonin is most effective for treating acute migraine in children and adolescents who have episodic migraine. We will identify the most effective dose to pull forward into a future fully-powered placebo-controlled efficacy study. If both doses are equally effective, we will bring forward the best tolerated dose. If doses are equally well tolerated, we will bring forward the lowest effective dose, as this will minimize cost to families should this treatment become widely adopted.
PRIMARY OBJECTIVE	To determine a change in mean VAS score between baseline and 2-hr time point in low-dose vs. high-dose group.

SECONDARY OBJECTIVES	
 • To determine a change in mean VAS score between baseline and 2-hr time point in low-dose vs. high-dose group in the < 40 kg and the ≥40 kg subgroups. (We will also do sensitivity analyses of completers who were awake for the 2-hr time point). • To determine the tolerability/side effects of high-dose vs. low-dose in the group over all, and in weight-based strata. • To determine the proportion of participants who get to mild/no pain by 2 hrs (overall and by weight group), and who remain at mild/no pain from 2-24 hours • To determine the proportion of participants who get to mild/no of each of: pain, photophobia, phonophobia, nausea, vomiting at 30, 60, 90, and 120 minutes and 24 hours; both overall and in weight based strata. • To determine the proportion of parents/participants who found the treatment useful, and who preferred it over other treatments they'd tried. • Using logistic regression, we will examine for possible predictors of treatment efficacy (sex, age, nap, nap duration, etc). • To determine the proportion of participants who needed rescue medication between 2-24 hrs, both overall and by weight- based strata.
NUMBER OF SUBJECTS	100
SUBJECT SELECTION CRITERIA	
Inclusion Criteria:
 
 1. Meet ICHD criteria for episodic migraine in children and adolescents, with at least 1 migraine attack per month on average. 2. Age 3-17 years 3. Dissatisfaction with previous acute treatments, for one or more of the following reasons: a) One or more previously tried acute medications have not been effective, or adequately effective, b) previously tried acute treatments have caused side effects, or C) patient/family would prefer a natural supplement for acute treatment over medication treatment 4. If of driving age, teen participant agrees not to drive for at least 8 hours after treating with melatonin. 
Exclusion Criteria:
 
 1. Allergy or intolerance to melatonin, or to chocolate. 2. Opioid or barbiturate overuse as defined in ICHD 3. Pregnant/lactating

TEST PRODUCT, DOSE, AND ROUTE OF ADMINISTRATION	Good Day Chocolate melatonin 1-8mg per attack, taken my mouth
CONTROL PRODUCT, DOSE AND ROUTE OF ADMINISTRATION	N/A
DURATION OF SUBJECT PARTICIPATION AND DURATION OF STUDY	Participation duration depends on how long it takes to treat two migraine headache attacks. In total, it will take approximately 2-3 hours to complete the study. Enrollment will take place over 24 months.
CONCOMITANT MEDICATIONS	
Allowed: All
 
Prohibited: N/A
 
Acute migraine medications such as ibuprofen (Motrin), acetaminophen (Tylenol), naproxen (Aleve) or a triptan (for example, sumatriptan) may be taken during the study, but we will ask participants to try to wait 2 hours after they take the study treatment, in order to see if the study treatment is effective.

EFFICACY EVALUATIONS	VAS pain scores between baseline and 2-hr time point
PRIMARY ENDPOINT	To determine a change in mean VAS score between baseline and 2-hr time point in low-dose vs. high-dose group.
SECONDARY ENDPOINTS	
 • To determine a change in mean VAS score between baseline and 2-hr time point in low-dose vs. high-dose group in the < 40 kg and the ≥40 kg subgroups. (We will also do sensitivity analyses of completers who were awake for the 2-hr time point). • To determine the tolerability/side effects of high-dose vs. low-dose in the group over all, and in weight-basedstrata. • To determine the proportion of participants who get to mild/no pain by 2 hrs (overall and by weight group), and who remain at mild/no pain from 2-24 hours • To determine the proportion of participants who get to mild/no of each of: pain, photophobia, phonophobia, nausea, vomiting at 30, 60, 90, and 120 minutes and 24 hours; both overall and in weight based strata.

	
 • To determine the proportion of parents/participants who found the treatment useful, and who preferred it over other treatments they'd tried. • Using logistic regression, we will examine for possible predictors of treatment efficacy (sex, age, nap, nap duration, etc). • To determine the proportion of participants who needed rescue medication between 2-24 hrs, both overall and by weight- based strata.
OTHER EVALUATIONS	Headache Diary
SAFETY EVALUATIONS	Incidence of adverse events.
PLANNED INTERIM ANALYSES	Serious adverse events will be monitored by the PI and the UCSF IRB on an ongoing basis throughout the study.
STATISTICS Primary Analysis Plan	To detect a mean difference of 3 cm (SD 3) on the change in VAS between doses, an effect size that has been considered clinically meaningful in previous pediatric migraine work, we would anticipate needing 2-hour outcome data on 16 individuals per arm for subjects treating only one attack. However, we will be able to control within subject variability to a degree by having subjects treat two attacks, and thus will revise the estimate to needing outcome data on 12 per group. We will use generalized estimating equations (GEE) to compare mean change from baseline to 2-hour time-points in high-dose vs. low-dose, controlling for repeated measures.
Rationale for Number of Subjects	
Assuming 15% drop-out, and adding an extra 20% data-loss for those who will be asleep at the 2-hour time point assessment, we anticipate needing to enroll 19 participants per dosing arm. As we wish to be able to perform this analysis both for the group overall (i.e. all “high dose” vs. all “low dose”), and for the <40 kg and ≥40 kg subgroups individually, we will need to enroll a total of 76 participants.
 
19 @ < 40 kg, given 1 mg at each of 2 attacks 19 @ < 40 kg given 4 mg at each of 2 attacks 19 @ ≥40 kg given 2 mg at each of 2 attacks 19 @ ≥40 kg given 8 mg at each of 2 attacks

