doses being studied here are well within the range of what has been safely studied in children before. We propose, depending on weight, to give between 1 mg and 8 mg of melatonin, once, at onset of headache. Each participant would treat two attacks. As noted above, neonates have safely been given 10mg/kg IV for peri-procedural pain management. Children undergoing auditory brainstem response tests were given 5-20 mg. Doses of 0.25-0.5 mg/kg have been given for MRI sedation—which would equate to about 15 mg for a 30 kg child. In another study, children were given 10 mg for MRI sedation. Our clinical experience suggests that for acute migraine treatment, 1-4 mg of melatonin would be adequate for children < 40 kg, and 2-8 mg for children and adolescents >40 kg. We propose to study a melatonin formulation that is an edible (i.e. chewable) milk-chocolate based formulation. We consider this formulation to have three potential advantages:

1. More rapid onset than a tablet/capsule formulation, potentially allowing for faster relief and in turn potentially a higher chance of relief, as treating when the pain is still mild has been shown to predict efficacy of other acute migraine treatments.
2. Young children who cannot yet swallow pills will be able to take this formulation.
3. Children who are nauseated during migraine attacks may still find a chocolate-based formulation palatable and be willing to take it during an attack.

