Chocolate melatonin supplies will be given to the parents for all young children who, in the opinion of the investigator, may need additional supervision. If a child were to eat all of the chocolate melatonin pieces at once, this would still be considered a safe amount, as neonates have been safely given 10mg/kg IV melatonin³.

They will also be given a paper headache diary (either in person or shipped). They will be instructed to treat as early as possible in an attack, i.e. ideally while the pain is still mild, however they will still be permitted to treat even if the pain has reached the moderate or severe levels. Participants will be asked to treat attacks that occur at home (or attacks that are not yet treated when they reach home), or that occur at another location where they can stay for at least 8 hours if needed, so as to ensure driving after dosing will not be necessary (for older teens), and that headache diaries will be available, and participants can sleep after dosing if desired.

Participants will record baseline pain intensity (and other migraine symptom intensity) at time zero, i.e. right before they dose the melatonin. They will be asked not to take other acute medications for two hours, and to record pain intensity (and other symptom intensity) at 30, 60, 90 min and the two-hour time marks. If they fall asleep, parents/caretakers will be instructed **not** to wake them for data collection, as sleep may be a mechanism by which melatonin helps acute

migraine. They will resume data collection as soon as they first awaken. They will be asked to collect data also at 4 hours and 24 hrs, and to record any acute medication used between 2-24 hours. They will also be asked to record their impressions about the treatment's efficacy, side effects, and whether or not they slept after dosing and if so for how long.

Study staff will contact participants until they complete the study to remind them about when to treat an acute attack and to answer any questions. Participants may be sent 'retention' packages (small office supplies, pens, or other small items) to remind them about the study. At the completion of the study, participants will be asked to mail back the headache diary in a pre-paid FedEx envelope. A \$5 gift card will be given to participants once they mail back the diary.

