14.2 Analysis of Primary Endpoint

We will use generalized estimating equations (GEE) to compare mean change from baseline to 2-hour time-points in high-dose vs. low-dose, controlling for repeated measures.

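### The 3 cm target is not tied to baseline pain, although families are asked to treat ideally while pain is mild; the scale's floor then shrinks the dose difference, and costs more power in the weight strata than in the pooled primary comparison

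*Combined protocol and SAP*

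**What the plan says.** The synopsis (Statistics, Primary Analysis Plan) sets the sample size "To detect a mean difference of 3 cm (SD 3) on the change in VAS between doses". It describes this as "an effect size that has been considered clinically meaningful in previous pediatric migraine work" and does not relate it to the baseline pain expected in this trial. From it come 16 evaluable per arm with one attack, then, with two attacks per child, "thus will revise the estimate to needing outcome data on 12 per group". The Rationale for Number of Subjects raises 12 to 19 enrolled per dosing arm. It applies this within each weight stratum, so that both the overall and the stratum comparisons can be made (76 in all).

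Section 10.1 governs when the dose is taken: "They will be instructed to treat as early as possible in an attack, i.e. ideally while the pain is still mild". The same sentence permits treatment once pain is moderate or severe. Section 1.2 also proposes "to give between 1 mg and 8 mg of melatonin, once, at onset of headache". Baseline pain is recorded at time zero, just before dosing, so the timing instruction largely determines the baseline.

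The primary analysis in section 14.2 is a GEE to "compare mean change from baseline to 2-hour time-points in high-dose vs. low-dose". No baseline covariate is named. The documents give no expected baseline distribution, no minimum baseline, no VAS range and no VAS cut-off for mild pain. Under the Study Design entry of the synopsis and section 2, doses judged equally effective are separated by tolerability and then by the lowest effective dose. No margin defines equality.

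**The concern.** A change score can fall only as far as the baseline allows. A child who doses at 2 cm can improve by at most 2 cm, whatever the dose. The target of 3 cm is a difference between two active doses, so it calls for more room than a mild attack has. The more closely families follow the timing instruction, the smaller the centimetre difference that a given true difference between doses can produce.

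The choice of dose for the next trial is at stake. Among attacks that improve, the floor pulls the contrast towards zero. With no margin for equality, a compressed difference is easily read as a tie, and a tie moves the choice away from efficacy.

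**Working it through.** **Inputs from the documents.** Difference 3 cm, SD 3; 16 per arm with one attack; 12 per group with two; 15% drop-out plus 20% data loss; 19 enrolled in each of four arms.

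**Assumptions.** VAS 0 to 10 cm; mild attacks start at a mean of 2 cm and moderate or severe ones at 6 cm; two-sided 5% and 80% power; within-child correlation 0.5. The plan states none of these. The last two assumptions are chosen because they reproduce its figures.

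**The plan's own figures.**
- One attack: n = 2(1.96 + 0.84)² × (3/3)² = 15.7, so 16.
- Two attacks: 15.7 × (1 + 0.5)/2 = 11.8, so 12.
- Enrolment: 12/(1 − 0.35) = 18.5, so 19.

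All three reproduce. The primary comparison pools the strata: 38 enrolled and about 2 × 12 = 24 evaluable per dose level.

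**The floor.** With equal baselines, the difference in change equals the low-dose 2-hour mean minus the high-dose 2-hour mean. The second term is at least 0, so a 3 cm difference needs a low-dose 2-hour mean of at least 3 cm even if every high-dose attack ends pain free. From a 2 cm start, low-dose pain would have to rise by 1 cm on average.

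**Mixed starts.** With a share m of mild starts, mean baseline b = 2m + 6(1 − m). If the low dose removes a fraction r of pain, the high dose must remove r + 3/b to give 3 cm. If the doses remove 75% and 25%, the difference is 0.5b.

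| Mild share | b (cm) | High-dose removal needed, r = 0 | Needed, r = 0.25 | Difference at 75% vs 25% (cm) |
|---|---|---|---|---|
| 0% | 6.0 | 50% | 75% | 3.0 |
| 30% | 4.8 | 63% | 88% | 2.4 |
| 50% | 4.0 | 75% | 100% | 2.0 |
| 70% | 3.2 | 94% | impossible | 1.6 |
| 100% | 2.0 | impossible | impossible | 1.0 |

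**Power.** SE = SD × √0.75 × √(2/n), with power from the noncentral t. At SD 3 the SE is 1.06 for n = 12 and 0.75 for n = 24. At SD 2 it is 0.71 and 0.50.

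| Difference (mild share) | Pooled primary, 24 per dose: SD 3 / SD 2 | Weight stratum, 12 per group: SD 3 / SD 2 |
|---|---|---|
| 2.4 cm (30%) | 88% / about 100% | 58% / 90% |
| 2.0 cm (50%) | 74% / 97% | 44% / 77% |
| 1.6 cm (70%) | 55% / 88% | 30% / 58% |

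For comparison, 3.0 cm at SD 3 gives 97% pooled and 77% in a stratum. The difference detectable with 80% power at SD 3 is 2.80 × 0.75 = 2.1 cm pooled and 2.80 × 1.06 = 3.0 cm in a stratum (normal approximation).

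**Does the SD shrink as well?** A simulation gave the high dose a 3 cm larger downward shift than the low dose before truncation to 0–10 cm, with an untruncated SD of 3.
- Mean baseline 2 cm, low-dose shift 0 to −2 cm: the observed difference falls to 1.7–1.0 cm and the SD to 2.0–1.5 cm. Power is 68%–48% with 12 per group and 94%–81% with 24.
- Mean baseline 6.5 cm, same shifts: difference 2.6–2.4 cm, power about 75% and 97%.

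The floor therefore reduces the centimetre estimate more than it reduces power.

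**The case against.** The strongest reply is that nothing here is a mild-only design. Section 10.1 states an ideal and then permits later treatment. It also accepts attacks not yet treated when the child reaches home. If half of attacks start mild and the low dose does nothing, a 3 cm difference needs 75% pain removal on the high dose, which is demanding but possible. This stands, and the loss depends on a mix that the documents do not give.

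Second, the primary comparison pools the strata. At about 24 evaluable per dose it keeps more than 80% power at 30% mild starts under either SD, and at 70% mild if the SD falls to 2. The 12-per-group figures belong to secondary objectives. This stands too.

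Third, the floor limits improvement only. If mild pain would otherwise grow over two hours, a high dose that holds it back can separate from a low dose that does not. With a low-dose rise of 2 cm and a high-dose fall of 1 cm from a 2 cm start, the simulated difference is 2.3 cm, with power 74% at 12 per group and 97% at 24. Whether the low dose is active is itself unknown.

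A reader might infer from the floor that the planned effect cannot be shown at all, or that the trial will call the doses equal whatever the truth. The documents do not support either inference, for these three reasons and because the SD shrinks along with the difference.

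What the reply does not remove is that the 3 cm target is unrelated to the baseline that the instruction produces, and that equality has no definition. Nor does the responder endpoint fill the gap, because an attack treated while mild already meets mild or no pain at time zero.

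**Conclusion.** The concern holds in a bounded form. The synopsis statistics and section 10.1 have not been reconciled: 3 cm is out of reach in mild-start attacks unless low-dose pain worsens, and a large proportional dose effect shows as 2.4 to 1.6 cm in the pooled data when 30% to 70% of attacks start mild. The consequence for power is moderate in the primary comparison (88% to 55% at SD 3; about 100% to 88% at SD 2) and larger in the secondary weight strata (58% to 30%; 90% to 58%). The main risk is misreading a compressed centimetre difference as evidence that the doses are equal.

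The direction follows from the scale and needs no model, provided that pain does not worsen on the low dose. The size rests on the assumed 2 cm and 6 cm starting means, the mild share, the same proportional relief in mild and severe attacks, and the correlation of 0.5.

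**What to change.** Leave the treatment instruction as it is.

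1. In section 14.2 and the SAP still to be written, keep the pooled GEE as the primary analysis and add time-zero VAS as a covariate. The covariate can improve precision but does not undo the floor.
2. Pre-specify a supplementary report of the dose contrast, with confidence intervals, by time-zero VAS (mild versus moderate or severe), with the cut-off fixed before analysis.
3. In the synopsis, state that the 3 cm target presumes enough baseline pain. Give the detectable difference at 80% power and SD 3 separately for the pooled comparison (about 2.1 cm) and for each weight stratum (about 3.0 cm), with the assumed alpha and correlation.
4. State in the carry-forward rule that a small or non-significant pooled difference does not by itself make the doses equally effective. Judge this on the confidence interval together with the contrast in moderate or severe starts.

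The cost is wording and one further analysis of data already collected. The moderate or severe subset has fewer attacks, a wider interval and less power than the pooled test, which is why it stays supplementary. The stated detectability in the strata also becomes less favourable to the plan once the baseline condition is attached.

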4 STUDY DESIGN

4.1 Study Overview

This randomized pilot trial is a dose finding study to determine which dose of melatonin is most effective for treating acute migraine in children and adolescents who have episodic migraine. Participants will be randomized to a higher-dose or a lower-dose, stratified by weight (< 40 kg and \geq 40 kg). They will treat 2 acute headache attacks and will complete a symptom diary for those 2 attacks and then return the diary to the study center. Randomization will be done in blocks of 4 to ensure equal group size and will be stratified by weight (< 40 kg or \geq 40 kg).

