8.3.4 Dosage/Dosage Regimen

19 participants @ < 40 kg, given 1 mg at each of 2 attacks
19 @ < 40 kg given 4 mg at each of 2 attacks
19 @ ≥40 kg given 2 mg at each of 2 attacks
19 @ ≥40 kg given 8 mg at each of 2 attacks

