12.4 Replacement of Subjects

Subjects who withdraw from the study treatment will not be replaced.

Subjects who withdraw from the study will not be replaced.

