14.4 Interim Analysis

There is no planned interim analysis.

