14.5 Sample Size and Randomization

Participants will be randomized based on weight (over or under 40kg). Randomization will be in blocks of 4. Nineteen participants per arm will be randomized in each of the four treatment arms.

- 19 @ < 40 kg, given 1 mg at each of 2 attacks
- 19 @ < 40 kg given 4 mg at each of 2 attacks
- 19 @ ≥40 kg given 2 mg at each of 2 attacks
- 19 @ ≥40 kg given 8 mg at each of 2 attacks

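### The synopsis plans 100 subjects, but the sample-size rationale derives 76 and Sections 8.3.4 and 14.5 list four arms of 19; nothing visible explains 100

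*Combined protocol and SAP*

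**What the plan says.** The Number of Subjects entry in the Protocol Synopsis reads "NUMBER OF SUBJECTS 100", with no note on whether this means consented, enrolled or randomised.

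The synopsis entry on the rationale for the number of subjects starts from 12 evaluable participants per group. It inflates that figure ("Assuming 15% drop-out, and adding an extra 20% data-loss for those who will be asleep at the 2-hour time point assessment") to 19 per dosing arm. Because the analysis is wanted in each weight stratum as well as overall, it concludes: "we will need to enroll a total of 76 participants".

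The body of the protocol follows the second figure. Section 8.3.4 lists four arms of 19, beginning "19 participants @ < 40 kg, given 1 mg at each of 2 attacks". Section 14.5 states "Nineteen participants per arm will be randomized in each of the four treatment arms" and repeats the list. Section 12.4 adds: "Subjects who withdraw from the study will not be replaced".

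**The concern.** A reader cannot tell from the protocol when recruitment is complete. A trial that stops at 76 has met Section 14.5 but is 24% short of the synopsis. A trial that runs to 100 enrols 24 more children and adolescents than the written justification supports.

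If one figure could be read as an allowance on top of the other, there would be no contradiction, so the possible explanations need checking. The weight subgroups are where the answer matters statistically: they are secondary endpoints, yet they are the stated reason for doubling the total from two arms of 19 to four.

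The study is also open label (Section 8.2), and the investigators review diaries for safety throughout (Section 5.3). A single target fixed in advance removes any later question about why enrolment closed when it did. Section 14.4 says "There is no planned interim analysis", and nothing in the documents suggests that closure would depend on results.

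**Working it through.** **Inputs from the synopsis statistics entries.** Difference 3 cm, SD 3; 16 evaluable per arm for one attack; 12 per group for two attacks; 15% drop-out plus 20% loss from sleep; four weight-by-dose arms.

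**Reproducing 76.**
- Losses added: 12 / (1 − 0.15 − 0.20) = 12 / 0.65 = 18.46, rounded up to 19; 4 × 19 = 76.
- Losses applied in sequence, rounding up each time: 12 / 0.85 = 14.12, so 15; 15 / 0.80 = 18.75, so 19; 4 × 19 = 76.
- Losses multiplied and rounded once: 12 / (0.85 × 0.80) = 17.65, so 18; 4 × 18 = 72. This does not match. The rationale's wording favours adding the losses, so 76 stands as the plan's own result.

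**Looking for 100.** No route from 12 per group reaches it. Starting from the one-attack figure, 16 / 0.65 = 24.62, so 25, and 4 × 25 = 100. But sequential rounding, which also yields 76 from 12, gives 16 / 0.85 = 18.82, so 19; 19 / 0.80 = 23.75, so 24; 4 × 24 = 96. A leftover from a one-attack calculation is therefore possible, but it is speculation.

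**Size of the gap.** 100 − 76 = 24; 24 / 76 = 31.6%; 1 − 76/100 = 24%.

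**Effect on power for 3 cm.** Assumptions not in the documents: two-sided alpha 0.05; between-attack correlation ρ = 0.5 (range 0.3 to 0.7); and, for 100, an even split of 25 randomised per arm. Power is from the noncentral t distribution.

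*Reading A: all 35% is lost at participant level.* Evaluable per arm: 19 × 0.65 = 12.35 and 25 × 0.65 = 16.25. The SD of a two-attack mean is 3 × √((1 + ρ)/2) = 2.60. The standard error is SD × √(2/n); pooling the two strata doubles n.

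*Reading B: 15% drop out, then each attack is lost to sleep independently with probability 0.20.* Retained per arm: 19 × 0.85 = 16.15 and 25 × 0.85 = 21.25. Both attacks survive with probability 0.64 and exactly one with probability 0.32. Information per retained participant is 0.64 / (9(1 + ρ)/2) + 0.32/9 = 0.130. The standard error is √(2 / (n × information)).

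| Comparison | SE at 76 | SE at 100 | Power at 76 | Power at 100 |
|---|---|---|---|---|
| Weight subgroup, A | 1.046 | 0.911 | 78% (73–84%) | 89% (85–93%) |
| Weight subgroup, B | 0.975 | 0.850 | 85% (81–88%) | 93% (91–95%) |
| Pooled primary, A | 0.739 | 0.645 | 97.8% | 99.6% |
| Pooled primary, B | 0.689 | 0.601 | 99.0% | 99.9% |

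Ranges in brackets are over ρ from 0.7 (lower power) to 0.3 (higher power).

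**Side point on equal arms.** Section 4.1 says "Randomization will be done in blocks of 4 to ensure equal group size". Under either total a stratum closes mid-block: 38 = 9 × 4 + 2 and, on an even split of 100, 50 = 12 × 4 + 2. If each block holds two per arm, the two assignments used from the last block fall in the same arm with probability 1/3, giving 20/18 or 26/24.

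**The case against.** The best defence is that this is one stray synopsis entry against three consistent statements. Those include the only written derivation and the operative Section 14.5, in a self-described pilot whose primary comparison is barely affected. That is right about the consequences, and it is why the point is no threat to the primary analysis. It does not make the two figures compatible: sample size is a core design parameter, and the synopsis is where many readers look for it.

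A second defence is that 100 could be a consent ceiling. The 15% and 20% are losses after enrolment, and Section 12.4 concerns withdrawals, so neither covers people who consent but are never randomised. This stands as a possibility. But no visible text says so, and the rationale speaks of enrolling 76. Some pages are missing from the public text, so the claim is limited to what can be read.

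Third, the power figures at 100 depend on 25 randomised per arm, which the documents do not state. With an uneven weight split, or if 100 means consented, they would not apply. That is a fair limit on them. The contradiction itself does not depend on them.

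Finally, the block-size remark holds whatever the synopsis says. It is a side point and carries no weight in the conclusion.

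**Conclusion.** The concern holds. The current text gives two planned sample sizes, 100 and 76, a difference of 24 participants. The figure of 76 follows from the protocol's own inputs, with no assumption about alpha or power; 100 has no stated basis. Attrition after enrolment and replacement of withdrawals do not account for it, and its origin cannot be established.

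The statistical consequence is negligible for the pooled primary comparison and moderate for the weight subgroups, where power differs by roughly 8 to 11 percentage points at ρ = 0.5, subject to the assumptions listed with the calculation. The entry should be corrected because it leaves the enrolment target undefined, and the correction is cheap.

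**What to change.** Change the Number of Subjects entry in the synopsis to 76, in line with the rationale and Sections 8.3.4 and 14.5. If 100 is a consent or enrolment ceiling, keep it but label it as such and say what the extra 24 allow for. Either is one synopsis entry in an IRB-approved amendment and adds no participants.

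If 100 randomised is truly intended, the rationale and Sections 8.3.4 and 14.5 must be reconciled to it with a stated basis and per-arm numbers. That costs 24 more participants than Section 14.5 lists.

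In the same amendment, describe the per-arm number as a target, since blocks of 4 do not guarantee exactly equal arms at these stratum sizes.
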